11 STUDY PROCEDURES

11.1 Subject Screening and Baseline Evaluation (Visit 1)

Subjects will be recruited for this study from MD Anderson. All subjects requiring latissimus dorsi muscle harvest procedures in conjunction with breast, scalp, upper extremity, or lower extremity reconstruction procedures will be screened for eligibility. The Investigator or a member of the research team will review the subject's medical history for eligibility and inclusion into the study. If all inclusion criteria are met and no exclusion criteria are present, the Investigator will inform the subject about the purpose of the study and will obtain written informed consent. The background of the proposed study along with the benefits and risks will be explained to the subject and questions will be answered. The subject must sign an informed consent that has been approved by the MD Anderson Institutional Review Board (IRB). Failure to provide informed consent renders the subject ineligible for the study.

The Investigator or a member of the research team will record the subjects' medical history and demographic information on a case report form tool. Protocol specific data and adverse events will be entered into the MD Anderson REDCap™ database. The first assessment of adverse events will take place in the operating suite at the time of surgery

and will continue for 6 months following surgery. The medical history will include information about previous treatments to further ensure compliance with the inclusion and exclusion parameters. The Investigator will conduct a medical history review and a physical exam. A pre-anesthesia appointment will also be coordinated. The Investigator or a member of the research team and subject will also complete a QuickDASH questionnaire. The subject will also undergo a physical therapy assessment to test the range of motion and strength of the shoulder to be used as a baseline postoperatively. As standard of care for patients undergoing these procedures, a pregnancy test will be ordered by the Anesthesia Department for appropriate female patients. This visit may be completed within 30 days prior to treatment/surgery.

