11.2 Treatment (Visit 2)

The subject will be taken to the operating room for surgery under general anesthesia with no muscle paralysis. The robotic-assisted latissimus dorsi harvest procedure will be performed as described in the protocol and will be videoed and/or photographed. Medications used, port placements, procedural details, adverse events and device details will be documented on the CRFs (Appendix H). Muscle flap viability will be assessed by clinical examination and doppler assessment prior to the reconstruction procedure. Such assessments will be documented in the CRFs (Appendix H) prior to the standard surgical breast, scalp, upper extremity, or lower extremity reconstruction procedure.

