11.3 Follow Up Evaluations (Visits 3-6)

Patients will be seen in the office for a visit within 0-2 weeks and then within 2-4 weeks after the surgical procedure. The next visit will be between 1-3 months after the procedure. The final visit will be between 3-6 months after the procedure. At these postoperative visits, incisions and drain sites will be checked and donor sites will be evaluated for adverse events. Additionally, pain assessments, the QuickDASH questionnaires, and the range of motion and strength tests will be administered. Drains will be removed as appropriate at approximately 2 to 3 weeks after the procedure.

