13 ADVERSE EVENT REPORTING

Adverse Event

An Adverse Event (AE) is any untoward medical occurrence, unintended disease or injury, or untoward clinical signs (including abnormal laboratory findings) in subjects, users or other persons, whether or not related to the investigational medical device. Note: This also includes events related to the study device and/or the study procedure. The U.S. Department of Health and Human Services, National Institutes of Health, National Cancer Institute, Common Terminology Criteria for Adverse Events (CTCAE), Version 4.03, will be used to grade adverse events.

All AEs related to the surgery that are observed by the Investigator or staff during a procedure, physical or laboratory examination, or mentioned by the subject either spontaneously or upon questioning will be recorded in REDCap™. Information pertaining to the recorded AE will be reviewed and verified by the IRB or its designated representative. The Investigator is responsible for assessing the severity of the AE, the causal relationship between any events and the clinical study procedure, activities or device. Additionally, the Investigator is responsible for providing appropriate treatment for the event and for adequately following the event until resolution. The following categories of adverse event severity are to be used by the Investigator:

- Mild: Awareness of a sign or symptom that does not interfere with the subject's usual activity or is transient, resolved without treatment and with no clinical sequelae;
- Moderate: Interferes with the subject's usual activity; and,
- Severe: Any fatal or immediately life-threatening clinical experience that requires a subject to be hospitalized, or hospitalization is unduly prolonged because of a

potential disability or danger to life or because an intervention has been necessitated. This includes any permanently disabling event.

The following categories of AE relatedness to the study device and procedure will be used by the Investigator:

- Possibly Related – may be related to study agent/device.
- Probably Related – is likely related to study agent/device.
- Definitely Related – is clearly related to study agent/device.

Adverse Device Effect (ADE)

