An Adverse Device Effect (ADE) is defined as an adverse event related to the use of an investigational medical device. Note: This definition includes adverse events resulting from insufficient or inadequate instructions of use, deployment, installation, operation or any deficiency of the investigational medical device.

Serious Adverse Event (SAE)

The following events (including laboratory results and outcome events) will be considered SAEs and must immediately (within 1 working day [24 hours] from the time the research team becomes aware of the event) be reported to the IRB as set forth in the MD Anderson AE Policy (Chapter 15 of the Human Subject Research Manual). These events must be reported whether or not the Investigator believes they are related to the study procedures or the device.

A serious adverse event is any adverse event that:

- results in death;
- is life-threatening, (places the subject at immediate risk of death from the event as it occurred);
- results in inpatient hospitalization or prolongation of existing hospitalization;
- results in persistent or significant incapacity or substantial disruption of a person's ability to conduct normal life functions;
- results in a congenital anomaly/birth defect; or
- based upon appropriate medical judgment, may jeopardize the subject's health and may require medical or surgical intervention to prevent one of the other outcomes listed in this definition.

Serious Adverse Device Effect (SADE)

An adverse device effect that has resulted in any of the consequences of a serious adverse event. This includes SADE's which by its nature, incidence, severity or outcome

has not been identified for the investigational study device. SADE's must be reported to Intuitive Surgical within 24 hours by telephone, fax and/or email.

Unanticipated Serious Adverse Device Effect (USADE)

This includes SADE's which by its nature, incidence, severity or outcome has not been identified for the investigational study device. USADE's must be reported to the IRB in accordance with Chapter 15 of MD Anderson's IRB Policy on Adverse Event Reporting and Management.

Unanticipated Adverse Device Effect (UADE)

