Any serious adverse effect on health or safety or any life-threatening problem or death caused by, or associated with, a device, if that effect or problem, was not previously identified in nature, severity, or degree of incidence in the investigational plan or application (including a supplementary plan or application), or any other unanticipated serious problem associated with a device that relates to the rights, safety, or welfare of subjects (21 CFR 812.3(s)).

Because no investigational drugs or regimens are used in this study, only Unanticipated Adverse Device Effects will be reported to the IRB and the IND Office. Events that are related to the neoadjuvant therapy or surgery will not be reported or recorded in the case report form.

All UADE will be reported to the IRB in accordance with the timeframes and procedures outlined in "The University of Texas M. D. Anderson Cancer Center Institutional Review Board Policy for Investigators on Reporting Unanticipated Adverse Events for Drugs and Devices".

Unless otherwise noted, the electronic SAE application (eSAE) will be utilized for safety reporting to the IND Office and IRB. Unanticipated Adverse Device Effects will be forwarded to FDA by the IND Sponsor (Safety Project Manager IND Office) according to 21 CFR 812.150.

It is the responsibility of the PI and the research team to ensure unanticipated adverse device effects are reported according to the Code of Federal Regulations, Good Clinical Practices, the protocol guidelines, the MD Anderson guidelines, and Institutional Review Board policy.

Device failure

Device failures which occur at the time of participant evaluation and which may prevent a participant from receiving therapy on trial will be kept on a log and will be reported as part of the annual report. Device failures at this point are not expected to affect patient safety, as participants may still receive appropriate therapy as determined by their attending physician.

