14.4 Data Collection

The Case Report Form (CRF) is the primary data collection instrument for the study. REDCap™ will be used as the electronic case report form. Primary data collection based on source documented hospital chart reviews will be performed clearly and accurately by the site personnel on the CRF. All missing data will be explained. If the item is not

applicable to the individual case, “N/A” will be written in the field. All entries will be printed legibly in black ink. To correct an error that has been made, a single line will be drawn straight across the incorrect entry and the correct data will be entered above it. All changes will be initialed and dated. A copy of the completed Case Report Forms will remain on site at the participating institution.

Study data will be collected and managed using REDCap (Research Electronic Data Capture) electronic data capture tools hosted at MD Anderson. [ref] REDCap (www.project-redcap.org) is a secure, web-based application with controlled access designed to support data capture for research studies, providing: 1) an intuitive interface for validated data entry; 2) audit trails for tracking data manipulation and export procedures; 3) automated export procedures for seamless downloads to common statistical packages; and 4) procedures for importing data from external sources. In the case of multi-center studies REDCap uses Data Access Groups (DAGs) to ensure that personnel at each institution are blinded to the data from other institutions. REDCap (<https://redcap.mdanderson.org>) is hosted on a secure server by MD Anderson Cancer Center's Department of Research Information Systems & Technology Services. REDCap has undergone a Governance Risk & Compliance Assessment (05/14/14) by MD Anderson's Information Security Office and found to be compliant with HIPAA, Texas Administrative Codes 202-203, University of Texas Policy 165, federal regulations outlined in 21CFR Part 11, and UTMDACC Institutional Policy #ADM0335. Those having access to the data file include the study PI and research team personnel. All protected health information (PHI) will be removed from the data when it is exported from REDCap for analysis. All dates for a given patient will be shifted by a randomly generated number between 0 and 364, thus preserving the distance between dates. Dates for each patient will be shifted by a different randomly generated number. Following publication study data will be archived in REDCap.

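### Section 13 contradicts itself on whether surgery-related adverse events enter the case report form and on which serious events go to the IRB

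*Combined protocol and SAP*

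**What the plan says.** **Recording.** The opening part of Section 13 (Adverse Event) covers "All AEs related to the surgery that are observed by the Investigator or staff during a procedure", at an examination, or through the subject's own account, and directs that they be recorded in REDCap. Section 14.4 states that "REDCap™ will be used as the electronic case report form". Section 11.1 agrees: "Protocol specific data and adverse events will be entered into the MD Anderson REDCap™ database", with assessment running from the operating suite to 6 months after surgery. Section 11.2 has adverse events at the operation documented on the CRFs. At the postoperative visits "donor sites will be evaluated for adverse events" (Section 11.3), and the Section 11.4 schedule marks adverse event assessment at Visit 2 and at Visits 3-6.

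The UADE part of Section 13 says the reverse: "Events that are related to the neoadjuvant therapy or surgery will not be reported or recorded in the case report form".

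**Reporting to the IRB.** The SAE part of Section 13 requires serious adverse events to reach the IRB within one working day (24 hours) and adds: "These events must be reported whether or not the Investigator believes they are related to the study procedures or the device". The UADE part says that "only Unanticipated Adverse Device Effects will be reported to the IRB and the IND Office", giving as its reason that the study uses no investigational drug or regimen.

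**Use in the analysis.** Donor-site complications through 6 months are the first secondary endpoint (Section 8.3). Section 12 promises the donor-site morbidity rate with a 95% confidence interval, bases part of the safety evaluation on donor-site adverse events, and refers the documentation of all adverse events to Section 13.

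**The concern.** The same kind of event and the same record receive opposite instructions, and the same serious event is both reportable and not reportable to the IRB.

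Two things are at stake. The first is safety oversight. A serious complication that was foreseen goes to the IRB under one part of Section 13 and is withheld under another. The second is the donor-site result. If the UADE-part sentence were followed, and surgery taken to include the robotic harvest, the events counted in secondary endpoint 1 would be under-recorded and the reported rate would be too low, in a study whose purpose is safety and feasibility.

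Flap failure has its own definition and stopping rule (Sections 12 and 14.7). No claim is made about it here.

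**Working it through.** The point is mainly textual, and the plan states no figure to reproduce. The steps set the rules side by side and then illustrate the possible size.

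**1. Do the recording rules concern the same record?** Yes. One names REDCap and the other the case report form, and Section 14.4 makes REDCap the electronic case report form.

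**2. Do they concern the same events?** Both refer to events related to surgery, without qualification. Section 2 separates the robotic harvest from the manual reconstruction, but the UADE-part sentence does not use that distinction, and both take place at Visit 2 (Section 11.4). Neoadjuvant therapy is mentioned nowhere else in the protocol, which suggests text carried over from another study. That is an inference; it would explain the sentence but not cure it.

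**3. Do the IRB rules differ in practice?** Section 10.1 lists pulmonary embolism, bleeding that may need transfusion, and flap loss among the standard harvest risks. Section 13 defines a UADE as a serious effect not previously identified in nature, severity or degree of incidence. A listed risk would ordinarily fall outside that definition, unless its severity or frequency was unexpected. When serious, it must be reported under the SAE part and is not reported under the UADE part.

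**4. Does the text say which rule prevails?** No. The phrase in the UADE part that allows for exceptions governs only use of the electronic SAE application, not which events are reportable.

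**5. Illustration of size.** Inputs: n = 15 (Section 9.3) and the background series in Sections 3.2 and 4.2.

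- Effect of one affected subject left unrecorded: 1/15 = 6.7 percentage points.
- Low end: no donor-site hematomas or seromas in 10 endoscopic free-flap patients (Section 3.2) or in 15 robotic patients (Section 4.2).
- High end: donor-site complications in 12 of 39 patients in an endoscopic partial-mastectomy series (Section 3.2). 12/39 = 30.8%, and 0.308 × 15 = 4.6 subjects.
- The range is therefore about 0 to 4.6 affected subjects in 15. The two ends count different outcomes, so the range is rough.

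Exact (Clopper-Pearson) 95% intervals near the high end, where the number missed is an assumption:

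| Scenario | Count recorded | Rate | 95% CI |
|---|---|---|---|
| All 5 recorded | 5/15 | 33.3% | 11.8 to 61.6% |
| 2 of the 5 missed | 3/15 | 20.0% | 4.3 to 48.1% |
| All 5 missed | 0/15 | 0% | 0 to 21.8% |

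At the low end little or nothing is lost.

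**The case against.** The strongest reply is that the recording conflict is unlikely to do harm. Sections 11.1, 11.2, 11.3, 11.4, 12 and the opening of Section 13 all call for these events to be assessed or recorded, against one sentence that looks out of place. Section 12 also lists seroma, wound dehiscence, delayed healing and flap loss as outcome variables, so donor-site data do not depend on the adverse event rules alone. Its cross-reference to Section 13 can be read as classifying events already captured. Because the sentence pairs surgery with neoadjuvant therapy, it may mean background cancer treatment, in which case harvest events remain recordable. Sections 17 and 18 make the sponsor and the investigator each responsible for proper reporting of all adverse events. The institutional IRB policies cited in Section 13 are not in the documents and might settle which rule prevails.

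Much of this stands as a limit on the consequence. The bias arises only under one reading of surgery, its size is a scenario and not an estimate, and it touches a descriptive secondary rate in a 15-subject pilot with no hypothesis test (Section 12.1). The absence of a precedence rule can be asserted only of the protocol text.

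None of it removes the contradiction. The sentence does not contain the narrow reading of surgery, and applied literally to the case report form it would reach the Section 12 outcome variables too. Narrowing surgery also leaves the restriction of IRB reporting to UADEs in direct conflict with the SAE rule.

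**Conclusion.** The concern holds: Section 13 is wrong as written on two counts, and it must be fixed.

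- **IRB reporting:** an anticipated serious event must be reported under the SAE part and is excluded under the UADE part. This conflict does not depend on how surgery is read, and it is the stronger reason to act, because it governs a mandatory safety duty.
- **Recording:** the UADE-part sentence contradicts the opening of Section 13 as well as Sections 11.1, 11.2 and 14.4. If it were followed with surgery taken to include the harvest, the donor-site rate would be biased downward by 6.7 percentage points for each affected subject missed. The total cannot be calculated from the documents; on the illustrative background rates it runs from nothing to the loss of about five subjects in 15.

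**What to change.** 1. Delete the sentence that bars surgery-related events from the case report form, or reconcile it with Sections 11.1 and 11.2 and the opening of Section 13. The result should be that all adverse events related to the harvest or surgery are recorded in REDCap through 6 months and feed the donor-site morbidity rate.
2. State what surgery covers: the robotic harvest, the manual reconstruction, or both. Remove the reference to neoadjuvant therapy unless it has a purpose in this study.
3. Separate the two duties: what is recorded in the case report form, and what is sent on an expedited basis to the IRB and the IND Office.
4. Reconcile the UADE-only sentence with the SAE rule, so that each class of event has one stated reporting route.

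The cost is protocol wording only. The recording is already called for elsewhere in the protocol, so no new data collection is needed.

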Patient information including age, gender, body mass index (BMI), medical history, history of radiation, history of smoking, defect characteristics (such as "partial breast, scalp, upper extremity, or lower extremity"), donor site morbidity, and functional deficits will be summarized. The rate of donor site morbidity and their 95% confidence interval will be reported.

Operative Variables: Length of surgery, type of defect, size of defect, type of reconstruction, length of incision used, length of robotic portion of the procedure, robotic instrumentation used, port placement. This information will be documented by the OR staff during surgery, and collected by the research team after surgery on standardized CRFs.

Outcome Variables: Length of stay, pain medication requirements, postoperative complications (such as seroma, wound dehiscence, delayed wound healing, or flap loss), length of time drains are required in donor site, and postoperative return to normal function, as well as, any residual functional deficits, defined as a subjective decrease in strength, range of motion or restriction in activities of daily living will be assessed at

between week 0-2, and between week 2-4 after the procedure. The subject will then have an evaluation at 3 months after the procedure. The subject's last follow up visit will occur 6 months post-procedure.

The safety of the robotic-assisted latissimus dorsi procedure will also be evaluated based on adverse events related to the donor site through 6 months post-procedure. Acute complications include but are not limited to: seroma; hematoma; overlying skin damage; and, injury to the muscle or vascular pedicle. All adverse events will be further categorized and documented according to section 13 of this clinical protocol.

The feasibility of the procedure will be evaluated based on the number of successfully completed robotic-assisted latissimus dorsi harvest procedures among the total attempted procedures. Any procedure that is abandoned or converted to an open surgical or endoscopic technique after being initiated with the *da Vinci*® robotic surgical system will be considered a failed *da Vinci*® procedure. The rate of successfully completed harvest procedure will be calculated along with its 95% CI.

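### Section 13 both requires and forbids recording surgery-related adverse events on the case report form, and gives two incompatible rules for reporting serious events to the IRB

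*Combined protocol and SAP*

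**What the plan says.** **Recording.** The Adverse Event subsection of Section 13 covers "All AEs related to the surgery that are observed by the Investigator or staff during a procedure", and also those found on examination or mentioned by the subject. It directs that they be entered in REDCap. Section 14.4 says that REDCap "will be used as the electronic case report form". The UADE subsection of Section 13 says: "Events that are related to the neoadjuvant therapy or surgery will not be reported or recorded in the case report form".

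**Reporting to the IRB.** The SAE subsection requires SAEs to reach the IRB within one working day (24 hours) of the team's becoming aware of them. It adds: "These events must be reported whether or not the Investigator believes they are related to the study procedures or the device". The UADE subsection says that "only Unanticipated Adverse Device Effects will be reported to the IRB and the IND Office".

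**Other recipients.** Serious adverse device effects (SADEs) "must be reported to Intuitive Surgical within 24 hours by telephone, fax and/or email". UADEs are forwarded to FDA. Unless noted otherwise, "the electronic SAE application (eSAE) will be utilized for safety reporting to the IND Office and IRB".

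**Link to the analysis.** Section 8.3 makes donor-site complications to six months the first secondary endpoint. Section 12 reports donor-site morbidity as a rate with a 95% confidence interval, and bases part of the safety evaluation on donor-site adverse events. On how events are handled it says: "All adverse events will be further categorized and documented according to section 13 of this clinical protocol".

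**The concern.** Both recording rules concern the same class of event and the same record. One includes those events and the other excludes them. Both IRB rules concern the same recipient. One sends every SAE and the other sends UADEs only. Staff who follow one sentence breach the other.

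Two things are at stake. First, this is a safety and feasibility study of a surgical technique, so the harms it most needs to count are surgical. If the exclusion were applied, seroma, hematoma and pedicle injury could be left out of the data behind the donor-site rate and its interval. Second, a serious harm that the protocol already anticipates need not be a UADE, so the restrictive sentence would keep it from prompt IRB review. Section 14.7 says that no DSMB will review the trial and gives monitoring to the IND Office and the Principal Investigator, which leaves more resting on clear reporting lines.

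**Working it through.** The plan states no figure on this point and no arithmetic applies. The check sets the rules side by side and runs two example events through them.

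**Step 1: do the recording rules concern the same record?** Yes. One names REDCap and the other names the case report form, and Section 14.4 makes these the same thing.

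**Step 2: do they concern the same events?** Both use the word *surgery*. Elsewhere the protocol uses it for the study operation:
- Section 11.1 starts adverse event assessment in the operating suite at the time of surgery.
- Section 11.2 takes the subject to the operating room for surgery, meaning the robotic harvest.
- Section 14.7 counts the 72 hours for flap failure from surgery.

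Mastectomy cannot be the meaning for all subjects, because Section 9.4.1 also admits scalp, upper extremity and lower extremity patients. Neoadjuvant therapy is mentioned nowhere else in the document, so the sentence may have been carried over from another protocol. Nothing in the text limits it to background treatment.

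**Step 3: run two events through the rules.**

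| Event | Earlier text in Section 13 | UADE subsection |
|---|---|---|
| Non-serious donor-site seroma seen at follow-up | Surgery-related, so entered in REDCap | Surgery-related, so neither reported nor recorded |
| Pneumothorax that prolongs the hospital stay | An SAE, so to the IRB within one working day | Already listed as a risk in Section 10.1, so it need not be a UADE. If it is not, it does not go to the IRB |

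Both events receive opposite instructions. The second result also holds for other risks listed in Section 10.1, such as bleeding that needs transfusion, pulmonary embolism and pedicle thrombosis, when they are serious and not unanticipated in nature, severity or incidence.

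**Step 4: does another section settle it?** Section 12 does not, since it hands adverse event documentation back to Section 13. Sections 11.1 and 11.2 favour recording, but nothing says that they take precedence.

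**Step 5: what is the IND Office rule?** It is stated: UADEs only, in the same sentence that conflicts with the SAE rule. The eSAE sentence then names one electronic channel to both the IND Office and the IRB without saying which events it carries. An SAE filed through that channel for the IRB may or may not also reach the IND Office.

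**The case against.** The best defence has three parts.

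**The exclusion means background cancer care.** Paired with neoadjuvant therapy, *surgery* could mean the oncological operation. That is plausible as an intention, but the text does not say it, and the same section uses the same word for events that must be recorded.

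**Practice would follow the other sections.** Adverse events go into REDCap under Section 11.1 and onto the operative forms under Section 11.2. Donor sites are checked at every postoperative visit under Section 11.3. Section 12 lists seroma, wound dehiscence, delayed healing and flap loss as outcome variables in their own right. Under Section 14.5 the monitor compares source data with the forms. Flap failure has its own definition and stopping rule in Section 14.7. This part stands, and it limits the consequence. A reader might infer that the trial would lose its complication data altogether, but these sections make that unlikely.

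**The IND Office is covered.** This also stands. A reader might infer that Section 13 has no rule on which events go to the IND Office. It has one, UADEs only. The gap is narrower: whether SAEs filed for the IRB also arrive there.

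A reader might also try to size the loss from the cited endoscopic series in Section 3.2, in which 12 of 39 patients had donor-site complications. That series treated partial mastectomy defects with an average follow-up of 3.67 years, against six months here, and its count includes hypertrophic scarring and a persistent sinus tract. Section 3.2 also cites 10 endoscopic patients with no donor-site complications such as hematoma or seroma, and Section 4.2 reports no donor-site hematoma or seroma in 15 robotic patients. No document says what share of events staff would leave out. Any modelled rate would rest on assumption alone.

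**Conclusion.** Section 13 is wrong as written in two places: on recording surgery-related events, and on which serious events go to the IRB. Both contradictions lie in current text and can be seen without any assumption about rates. The likely consequence is uneven recording of donor-site harms and late IRB reporting of anticipated serious ones. The size of that effect cannot be estimated from the documents. The judgement that total loss is unlikely assumes that staff give weight to Sections 11, 12 and 14.5 over the exclusion. The matter should be corrected because it touches a secondary endpoint and the reporting of serious harm, but it does not undermine the design.

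**What to change.** 1. **Recording.** Delete the sentence that excludes events related to neoadjuvant therapy or surgery. If the sponsor wants an exclusion, limit it to named background cancer treatments and state that harvest, donor-site, flap and reconstruction events are always recorded. Keep the scope of the Adverse Event subsection, which covers all surgery-related events. Narrowing it to harvest or device events could drop harms attributed to the reconstruction, such as pedicle thrombosis after a free transfer, which bears on the primary safety endpoint.
2. **Reporting.** Replace the UADE-only sentence with one rule per recipient:
   - IRB: all SAEs, within the existing one-working-day limit, and UADEs.
   - Manufacturer: SADEs, within 24 hours.
   - IND Office: UADEs, with an explicit statement of whether SAEs filed through eSAE also go there.
   - FDA: UADEs, as now.

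Whether all SAEs go to the IND Office is the sponsor's choice. No current text requires it, and resolving the contradiction needs only that the answer be written down.

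The cost is a wording amendment to two sentences of Section 13. REDCap, eSAE and the event definitions are already in the protocol, so no new visit, form or committee is needed.
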